3. STATISTICAL ANALYSES

3.1. General Considerations

All data from scheduled and unscheduled visits will be presented in the subject listings.

However, unless noted otherwise, only data from scheduled/windowed visits will be included in the summaries, statistical analysis, and calculation of derived parameters.

Summary tables and listings (e.g., post text tables and individual subject data listings are prepared according to ICH Guideline E3) include a “footer” providing explanatory notes.

Continuous variables will be summarized using an 8-point descriptive summary (number of subjects [n], mean, standard deviation [SD], median [Q2], interquartile range [25th percentile Q1, 75th percentile Q3], minimum, and maximum) unless otherwise indicated. Categorical variables will be summarized by frequency and percentage of subjects in each category. All summaries will be presented by treatment and visit when applicable.

For binary endpoint comparisons to placebo when the expected number of responders/non-responders are less than 5 per treatment groups being analyzed a fishers exact test will be performed. For safety assessments, summary statistics will be reported by treatment.

Analyses and tabulations will generally be prepared using SAS®, version 9.4 or later.

3.1.1. Baseline Definition

In general, the baseline value for efficacy variables and for safety variables is the value associated with the last available pre first dose visit/time point at which the variable was to be collected according to the schedule of study procedures, and must have been collected prior to first dose.

The exceptions are for fecal samples and electronic tablet data that can be submitted within 3 days of first dose.

3.1.2. Study Day

If the assessment occurs on or after the first dose date then induction study day will be calculated as (date of assessment – date of first dose/randomization) + 1.

If the date of interest occurs prior to the first dose date then induction study day will be calculated as (date of assessment – date of first dose).

There is no induction study day 0.

ATE study day will calculated in a similar manner with first dose in ATE period used to calculate the day (expected to be ATE Day 1).

3.1.3. Visit Windows

All assessments will be summarized using analysis windows.

The terminology of unscheduled will be applied to assessments that are outside an analysis window regardless of the nominal label associated with the assessments in the EDC system.

The following visit windows will be used in the summary of clinical data.

Table 6: Visit Analysis Windows

Nominal Visit	Nominal Day	Start (days)	Stop (days)
Screening	NA	-28	-1
Baseline	1	1	Induction Day 1
Week 4	Induction Day 28	Induction Day 21	Induction Day 35
Week 8	Induction Day 56	Induction Day 49	Induction Day 63
Week 12	Induction Day 84	Induction Day 77	Earliest of: 
 • ATE Day 1 dose date • Induction Day 98 (Induction Day 112 for SES-CD score)
ATE Week 4	ATE Day 28	ATE Day 21	ATE Day 35
ATE Week 8	ATE Day 56	ATE Day 49	ATE Day 63
ATE Week 16	ATE Day 112	ATE Day 105	ATE Day 126
ATE Week 24	ATE Day 168	ATE Day 161	ATE Day 182
ATE Week 36	ATE Day 252	ATE Day 245	ATE Day 266
ATE Week 48	ATE Day 336	ATE Day 329	ATE Day 350

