6.3.15. Early Study Drug Discontinuation

Subjects who prematurely discontinue the study drug due to adverse events (AEs), lack of response, or any other reason besides withdrawal of consent during Induction or ATE will be asked to return for an Early Study Drug Discontinuation visit. This visit will be conducted within 5 days after the last dose of study drug, if possible. Subjects will also return for the EOS visit for collection of safety data and assessment of disease activity.

During ATE, subjects should be assessed for clinical benefit and if there is no clinical benefit, as deemed by the investigator, the subject should stop study drug treatment and be withdrawn from the study.

Subjects should be instructed to fast from food and non-clear fluids on the evening prior to the Early Study Drug Discontinuation visit to ensure a minimum 8-hour fast prior to the fasted blood sample collection.

The following procedures will be performed at the Early Study Drug Discontinuation visit:

- Tobacco use status
- Vital signs
 - Heart rate (HR) and systolic and diastolic blood pressure (BP)
 - Respiratory rate
 - Body Temperature
- 12-lead ECG
- Physical examination to be conducted according to local practice
- Fistula drainage assessment (if applicable) to determine the number of fistula and confirm draining is occurring.
- Weight
- Blood collection
 - Hematology
 - Serum chemistry
 - Overnight fasting lipid panel
 - [REDACTED]

- [REDACTED]
- Urine collection
 - Urinalysis
 - Pregnancy test for females of childbearing potential – If urine b-hCG test is positive, confirmation with serum b-hCG test is required
 - Fecal collection [may be collected within 3 full days (approximately 72 hours) prior to the visit; however, it is preferable that the stool sample be collected during the first bowel movement in the morning]
 - [REDACTED]
 - Disease Assessments
 - CDAI Components
 - Abdominal Pain and Total Stool Frequency Scores
 - [REDACTED]
 - [REDACTED]
 - Perform drug accountability and review subject's compliance with study drug dosing
 - Review concomitant medications
 - Adverse event assessment (AEs, SAEs, Adverse Events of Special Interest)
 - Review diary completion and compliance; counsel subject as needed Description of Study Assessments

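### The SAP's Induction visit windows have gaps and no rule for the Early Study Drug Discontinuation visit, so discontinuation assessments can fall outside the primary model and by-visit summaries

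*SAP*

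**What the plan says.** SAP 3.1.3 opens its window rule with "All assessments will be summarized using analysis windows". In the Visit Analysis Windows table, Week 4 runs from "Induction Day 21" to Day 35, Week 8 from "Induction Day 49" to Day 63, and Week 12 from "Induction Day 77" to the earlier of the ATE Day 1 dose and Day 98 (Day 112 for SES-CD). There is no row for Early Study Drug Discontinuation or End of Study. Of records outside these ranges it says "The terminology of unscheduled will be applied to assessments that are outside an analysis window regardless of the nominal label associated with the assessments". SAP 3.1 states that, unless noted otherwise, "only data from scheduled/windowed visits will be included in the summaries, statistical analysis, and calculation of derived parameters". The readable text of the SAP makes no exception for discontinuation visits.

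Protocol 6.3.15 schedules CDAI components, labs, vital signs and an ECG for a subject who stops early: "This visit will be conducted within 5 days after the last dose of study drug, if possible". The visit can therefore fall on any Induction day.

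Four other SAP rules bear on the point:
- 3.3.4.1: the primary estimand is treatment policy. Data after an intercurrent event, including stopping study drug, are used as collected.
- 3.1.5.1: Induction analyses end at last dose + 5 days, or at the ATE Day 1 dose if that is earlier.
- 3.1.4: when records share a window, the one nearest the nominal day is used; for labs it is the latest.
- 3.3.4.2: the primary model uses Weeks 4, 8 and 12 only.

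**The concern.** A subject who stops drug in Induction has two later CDAI assessments under the protocol: the discontinuation visit and the End of Study visit about four weeks after last dose. SAP 3.1.5.1 removes the second from Induction analyses. The discontinuation CDAI is then often the only post-stop value that a treatment-policy analysis could use, and whether it is used depends on the calendar day of the stop.

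Where it is not used, the primary model fills in the subject's course under missing at random from earlier visits alone. The only sensitivity analysis aimed at the missing-data assumption (SAP 3.3.5.1) is an ANCOVA on observed Week 12 values, in which such a subject carries no weight. A subject whose only postbaseline CDAI is at a discontinuation visit before Day 21 may count as mITT under SAP Section 2 and yet supply nothing to the model. For safety, by-visit summaries of labs, vital signs and ECGs lose the values taken at the stop.

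**Working it through.** The documents give no figure for window coverage, discontinuation rate or stopping times, so there is no stated figure to reproduce. The stated power (82% and 58%) does not involve the windows.

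**1. Uncovered days** (SAP 3.1.3). Days 2-20 = 19, Days 36-48 = 13, Days 64-76 = 13. The sum is 45. Share of Days 2-84: 45/83 = 54%. Share of the days before the Week 12 window opens (Days 2-76): 45/75 = 60%.

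**2. Discontinuation visits outside every window.** Assumption: last dose is equally likely on each of Days 1-83. The visit follows 0 to 5 days later (Protocol 6.3.15). A same-day visit on Day 1 is counted as unusable.

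**3. Discontinuation CDAIs unused.** Add the in-window visits that lose to an already attended Week 4 or Week 8 visit under the nearest-to-nominal rule. Assumption: those visits took place on Days 28 and 56. At lag 0, discontinuation visits on Days 29-35 and 57-63 lose (7 + 7 = 14). At lag 5, Days 33-35 and 61-63 lose (3 + 3 = 6).

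**4. Contiguous windows** (Week 4 = Day 15-42, Week 8 = Day 43-70, Week 12 = Day 71 to the existing limit). Uncovered days fall to Days 2-14: 13/83 = 16%. Steps 2 and 3 are repeated with the same selection rule.

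| Days from last dose to visit | Outside all windows, current | CDAI unused, current | CDAI unused, contiguous |
|---|---|---|---|
| 0 | 46/83 = 55% | (46+14)/83 = 72% | (14+28)/83 = 51% |
| 2 | 44/83 = 53% | (44+12)/83 = 67% | (12+26)/83 = 46% |
| 5 | 41/83 = 49% | (41+6)/83 = 57% | (9+20)/83 = 35% |

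Moving the attended visits to Days 29 and 57 lowers the lag-5 figures slightly, to 45/83 = 54% (current) and 27/83 = 33% (contiguous).

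**5. Dependence on timing.** If every discontinuation visit fell in Days 2-20, 100% would be outside the windows; if every one fell inside a window, 0%.

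**6. Subjects.** If 10-20% of 160 stop in Induction (assumption), that is 16-32 subjects. Then 16 × 0.49 ≈ 8 to 32 × 0.55 ≈ 18 have a discontinuation visit outside every window.

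**7. One case.** Last dose is on Day 40 and the visit on Day 42. Under the current table Day 42 is in no window, so the model sees only Week 4. Under contiguous windows Day 42 belongs to Week 4 but is 14 days from nominal, so an attended Day 28 visit is chosen instead. Contiguous windows alone do not bring this CDAI into the model.

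**The case against.** The strongest reply is that the loss is narrow. Every record stays in the listings (SAP 3.1). Treatment-emergent adverse events are counted by onset date up to last dose + 28 days (SAP 3.7.2), and AESIs are summarised as events. Maximum CTCAE grade is summarised through Week 12 rather than by visit, although the SAP does not say whether unscheduled labs count toward it. Protocol 8.8 keeps categorical findings from unscheduled times in whole-period summaries. All of this stands, and it confines the safety effect to by-visit summaries of labs, vital signs and ECGs.

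On efficacy, the 7-day margins around Weeks 4 and 8 already contain the protocol's -3 to +5 day visit windows, so on-time visits are captured. SES-CD is not collected at the discontinuation visit. For the binary endpoints, stopping for worsening disease or lack of benefit counts as non-response, and missing data are non-response except when due to COVID-19. Supplementary Estimand 1 sets change to zero after a treatment-failure event. A Day 42 CDAI is not a Week 12 value. These points also stand. They do not settle how the primary model treats a discontinuation CDAI.

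A reader might add the End of Study visit to the list of records lost to the gaps. The documents do not support that: SAP 3.1.5.1 already excludes it from Induction analyses, whatever the windows are.

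**Conclusion.** The point holds in limited form. The gaps and the missing rule are plain on the page. They cover 54% of Induction Days 2-84. With uniform stopping and attended Day 28 and 56 visits, 49-55% of discontinuation visits lie outside every window and 57-72% of discontinuation CDAIs are not used. These shares depend on stopping times that the documents do not give. The conflict with the treatment-policy estimand is the main reason to act.

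Two stronger readings are tempting. One is that the gaps bias the Week 12 comparison, because the model predicts from older and better values. Nothing in the documents shows that discontinuers were better at Week 4, or that the loss differs by arm; direction and size are unknown. The other is that safety assessments at discontinuation are discarded and the drug's safety profile looks cleaner. The listings and date-based event tables rule that out beyond the by-visit summaries.

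**What to change.** 1. Make the Induction windows contiguous, for example Week 4 = Day 15-42, Week 8 = Day 43-70 and Week 12 = Day 71 to the existing upper limit. State that discontinuation assessments are mapped into them by study day. Unused CDAIs fall to about 35-51% on the assumptions above.
2. Add an explicit rule for a discontinuation CDAI that shares a window with an attended visit. Assigning it to the next scheduled visit is one option; that can place a value up to 27 days from nominal (Day 29 assigned to Day 56).
3. State whether a CDAI outside all windows satisfies the mITT condition.
4. Reconcile the last dose + 5 days cut-off in SAP 3.1.5.1 with the treatment-policy estimand in 3.3.4.1.

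The cost is SAP text and reprogramming before lock, with no new data. There are two downsides. Under item 1 a mapped value can be about two weeks from its nominal day. Because SAP 3.1.4 takes the latest lab in a window, wider windows can also replace an on-time lab value with the discontinuation value, so the SAP should say whether that is intended.

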6. STUDY PROCEDURES

Study procedures will be performed only after written informed consent is obtained. The Screening visits (i.e., Stage 1 and Stage 2) will be performed within 35 days before dosing. One repeat Screening Stage 1 visit is allowed for each subject per the investigator's discretion. No more than one repeat Screening Stage 1 visit or repeat visit-specific procedure/assessment is allowed for each subject, unless prior written approval has been provided by the Sponsor. If the subject does not begin Induction treatment within this 35-day window, Screening evaluation procedures (i.e., Stage 1 and Stage 2) must be repeated. Subjects may be considered for re-screening of both Screening Stage 1 and Screening Stage 2 procedures, depending on the reason for the initial screening failure, per consultation with and approval from the Sponsor.

During the study, every effort should be made to perform study procedures as listed in the Schedule of Study Procedures (Table 1). Assessments will be made and biological samples will be taken in the following recommended order at those study visits at which they coincide: fecal sample collection, adverse event assessment, ECG, vital signs, [REDACTED] clinical laboratory safety samples, [REDACTED] and ileocolonoscopy with biopsies (although ileocolonoscopy should be done within 3 days prior to the Week 12 clinic visit). Study drug administration will be in-clinic on Day 1, Week 4, Week 8, Week 12, ATE Week 16, ATE Week 24, ATE Week 36, and ATE Week 48 after all pre-dose assessments [REDACTED] and procedures have been completed.

Throughout the study, the acceptable window for scheduled assessments is as follows:

- - 3 to + 5 days from the nominal visit date for Week 4, Week 8, ATE Week 4, ATE Week 8, ATE Week 16, ATE Week 24, ATE Week 36, ATE Week 48 and the EOS visits
- -1 to +3 days from the nominal Week 12 clinic visit for the Week 12 ileocolonoscopy with biopsies. The Week 12 ileocolonoscopy and biopsies should be performed on the same day as the Week 12 visit, preferably in the early morning, to permit morning dosing with study drug. However, if not feasible to perform both the ileocolonoscopy and the clinic visit on the same day, the ileocolonoscopy could be performed within 3 days after the Week 12 clinic visit. However, the Week 12 endoscopy must be performed at least 1 day prior to ATE Day 1.
- + 3 days from the nominal visit date for the Week 12 clinic visit

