6.3. Procedures by Visit

6.3.1. Screening

6.3.1.1. Screening Stage 1

Screening Stage 1 visit assessments will be performed between 35 and 1 days prior to Day 1. Initial eligibility assessments will be reviewed and confirmed by the investigator prior to each subject continuing on to the endoscopy with biopsy assessments at Screening Stage 2.

The following procedures will be performed at Screening Stage 1:

- Written informed consent (signed and dated) after the nature of the study has been explained and before any study procedure is performed
- Review of inclusion and exclusion criteria
- Medication and medical history
- Vital signs
 - Heart rate (HR) and systolic and diastolic blood pressure (BP)
 - Respiratory rate

- Body Temperature
- 12-lead ECG
- Physical examination (including fistula exam to determine drainage status if the subject has a fistula) to be conducted according to local practice
- Height and weight
- Chest X-ray (unless one has been performed within 3 months of Screening, documented to be negative, and reviewed by investigator. Subjects who have had a chest X-ray within 3 months prior to Screening will not require a repeat X-ray unless subject is deemed to be at high risk of recent pulmonary infection)
- Blood collection
 - Hematology
 - Serum chemistry
 - FSH (postmenopausal females)
 - Viral hepatitis and human immunodeficiency virus [HIV] serology panel (Refer to Section 6.4.14 for additional details)
 - QuantiFERON®-TB Gold [unless an exam has been done with negative findings within 90 days prior to Screening or subject has a history of latent TB that has been adequately treated within the prior 5 years (Refer to Section 6.4.15 for additional details)] - If the QuantiFERON®-TB Gold result is indeterminate, a repeat QuantiFERON®-TB Gold will be performed.
 - Labs required for Screening Stage 2 can be collected during this visit if the subject happens to be fasting during this visit. Subjects should not be instructed to come in fasting.
- Urine collection
 - Urinalysis
 - Pregnancy test for females of childbearing potential – If urine b-hCG test is positive, confirmation with serum b-hCG test is required
- Fecal collection
 - Fecal infectious studies [C. difficile, other bacteria (including Shigella, Salmonella, Yersinia, E. coli O157, and Campylobacter), and ova and parasite]
- Review concomitant medications
- Adverse event assessment (AEs, SAEs, Adverse Events of Special Interest)

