1.2. Study Design

1.2.1. Summary of Study Design

This study includes 3 phases: Screening, Induction, and Active Treatment Extension (ATE). Screening is up to 5 weeks long. The Induction phase of the study is a multi-center, randomized, double-blind, placebo-controlled, parallel-group study evaluating 2 dose levels of TD-1473 (80 mg or 200 mg; approximately 60 subjects per dose level) compared to placebo (approximately 40 subjects) for 12 weeks in subjects with moderately-to-severely active Crohn's Disease (CD).

Subjects who complete the Induction phase will continue to receive TD-1473 in ATE, either at 80 mg or 200 mg, for up to 48 additional weeks.

Figure 1: Study Design Schematic

Screening:

To determine eligibility, subjects will undergo assessments during the Screening period (up to 35 days prior to Day 1 dosing) as outlined in the Schedule of Study Procedures (Section 1.4). Disease activity will be assessed by the clinical scores, based on symptoms reported on a daily diary, which will be captured electronically beginning the day after Screening Stage 1.

Subjects who meet all inclusion (with the exception of the endoscopic subscore criterion) and no exclusion criteria, will undergo ileocolonoscopy with biopsies to complete Screening Stage 2. The aim of this endoscopic exam is to assess the SES-CD score by central reading and to obtain biopsies.

Induction

If the subject meets all eligibility criteria, the subject may be randomized into one of the following 3 treatment groups in a 3:3:2 ratio: TD-1473 80 mg, TD-1473 200 mg, or placebo.

The randomization will be stratified by prior biologics failure and CDAI score category (≤ 300 , > 300) at the Screening Stage 2 visit (using laboratory data from Screening Stage 1 for the score calculation). Approximately 40-60% of subjects randomized will have failed prior treatment with biologics. Subjects will be treated for 12 weeks and assessed for the various endpoints, including those that incorporate findings from an ileocolonoscopy and biopsies at the Week 12 visit. Corticosteroids will start to be tapered at Week 8. Subjects will undergo clinic study visits every 4 weeks in accordance with the Schedule of Assessments

(Section 1.4). During this time, subjects will continue to fill out a daily diary.

ATE:

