3.3.2. CDAI Score

CDAI score is calculated as sum of a Subscore x Multiplier from Appendix 5.2. The following subscores are calculated based on the most recent evaluable 7 days.

- Number of liquid or very soft stools subscore
- Average Abdominal pain subscore
- General well-being subscore

Evaluable days are defined as any non-missing diary days during the 10 days prior to the study visit. The day prior to endoscopy, day of endoscopy and the day following endoscopy will be treated as non-evaluable and treated as missing.

If fewer than 5 evaluable days data are available for any of the above subscores then the subscore is set to missing for that timepoint. If only 5 or 6 evaluable days' data are available for the above mentioned subscores then the subscore total is calculated as:

(Total score over available days/Number of available days)*7

The weight component of the CDAI will be based on ideal weight (see Section 5.3.1.4).

The CDAI score should be calculated for a visit only if ≥ 4 subscores are available at a visit, with missing subscores imputed by carrying forward the last non-missing subscore. If <4 subscores are available at a visit then the CDAI score will be set to missing.

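### SAP Table 6 opens the Screening window at Day -28 although screening is allowed from Day -35, so it is unclear whether early Stage 1 data, chiefly height, may enter derivations

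*SAP*

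**What the plan says.** **Window.** The Screening row of Table 6 in SAP 3.1.3 reads "Screening NA -28 -1". The same section says that "The terminology of unscheduled will be applied to assessments that are outside an analysis window regardless of the nominal label".

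**Use of data.** SAP 3.1 says that "unless noted otherwise, only data from scheduled/windowed visits will be included in the summaries, statistical analysis, and calculation of derived parameters".

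**Length of screening.** SAP 1.2.1 says that "subjects will undergo assessments during the Screening period (up to 35 days prior to Day 1 dosing". Footnote P to the SAP schedule of assessments also lets Stage 2 laboratory samples be taken from Day -35. Protocol section 6 agrees: "The Screening visits (i.e., Stage 1 and Stage 2) will be performed within 35 days before dosing". So does protocol 6.3.1: "Screening Stage 1 visit assessments will be performed between 35 and 1 days prior to Day 1".

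**Height.** Protocol Table 1 schedules height once, at Screening Stage 1. SAP 3.3.2 states: "The weight component of the CDAI will be based on ideal weight". Ideal weight comes from height by the formula in SAP 5.3.1.4.

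**Baseline.** SAP 3.1.1 takes the last available pre-dose visit at which the variable was due under the schedule, and sets no window. Protocol 8.1 admits both scheduled and unscheduled pre-dose assessments unless the SAP specifies otherwise.

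**The concern.** A subject whose Stage 1 visit falls on Day -35 to -29 has complied with the protocol. Table 6 still places that visit outside every analysis window, so its data become unscheduled whatever the EDC label says. The general rule in SAP 3.1 then keeps them out of summaries and derived parameters.

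Most Stage 1 measurements that matter to the analysis (weight, hematocrit, routine laboratory tests) are repeated on Day 1, so little is lost. Height is not. If the only height is set aside, ideal body weight cannot be computed. The CDAI weight item, BMI and ideal-weight creatinine clearance then have no input at any visit. Carrying forward cannot help, because there is no earlier value. SAP 3.3.2 does not say how to treat a CDAI item that was never observed.

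At stake is a component of the primary endpoint's score. Two programmers working from the same SAP could build different datasets.

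**Working it through.** **1. Day count.** Screening lasts up to 5 weeks: 5 × 7 = 35 days. Under SAP 3.1.2 a pre-dose study day is the assessment date minus the first-dose date, so the earliest permitted day is Day -35.

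Cross-check against total participation in the protocol synopsis: 5 + 12 + 48 + 4 = 69 weeks, as stated there. A 28-day screening would give 4 + 12 + 48 + 4 = 68. The documents therefore support 35 days, and the Day -28 in Table 6 is not reproduced.

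**2. Gap.** Permitted days: -35 to -1, which is 35. Windowed days: -28 to -1, which is 28. The gap is Day -35 to -29, and 7/35 = 20% of permitted days. This is a share of calendar days, not of subjects.

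**3. What remains of the CDAI if height is set aside.** SAP 5.2 lists eight items. Without the weight item seven remain, so the requirement of at least four in SAP 3.3.2 is met and a score is still called for.

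**4. Size of the weight item.** Ideal body weight (IBW) is 50 kg (male) or 45.5 kg (female) + 2.3 × (height − 152.4)/2.54. The item is 100 × (IBW − weight)/IBW, floored at -10, with multiplier 1. The documents give no distribution of height or weight, so the heights and weights below are assumed.

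| Sex, height | IBW (kg) | Item at 45 kg | at 55 kg | at 65 kg | at 80 kg | Change in item per 2 kg gain |
|---|---|---|---|---|---|---|
| F, 155 cm | 47.9 | 6.0 | -10 | -10 | -10 | -4.2 |
| F, 165 cm | 56.9 | 20.9 | 3.4 | -10 | -10 | -3.5 |
| M, 175 cm | 70.5 | 36.1 | 21.9 | 7.8 | -10 | -2.8 |
| M, 190 cm | 84.0 | 46.5 | 34.6 | 22.7 | 4.8 | -2.4 |

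The last column is -200/IBW and applies only where the floor does not bind.

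**5. Effect on the change score.** Suppose the item is absent at every visit and the score is the sum of the other seven. Its level then cancels in the change from baseline, and only its own change is lost. For a 2 kg weight change that is 2.4 to 4.2 points in an affected subject. The planned effects in SAP 1.5 are 45 and 60 points, and 4.2/45 = 9%. The treatment difference moves by less than that unless every subject is affected and the arms differ by 2 kg in mean weight change.

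**6. Effect on CDAI level.** Levels do not cancel. Omitting the item would score an affected subject up to 10 points too high (where the item is at its floor) or up to about 46 points too low (the extreme of the table). This bears on the below-150 criterion in CDAI remission and response (SAP 3.4.3). It also bears on the 300-point category used as a stratum in the CMH tests and as a factor in the SES-CD model (SAP 3.4.4.2).

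**7. SES-CD timing.** Take the earliest Stage 1, Day -35. The diary starts the next day (SAP 1.2.1), and at least five entries are needed before bowel preparation (schedule footnote V): Days -34 to -30. The day before colonoscopy does not count (protocol 6.4.25.2): Day -29. The earliest endoscopy is then Day -28, inside the window. Counting an entry on the Stage 1 day itself would reach Day -29 at most. A rescreened subject may reuse an endoscopy only if it is within 28 days of Day 1 (protocol 6.4.18).

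**The case against.** The best reply is that the exclusion rule opens with an exception, and that SAP 3.1.1 is that exception. It defines baseline by the schedule of procedures, which runs from Day -35, and not by Table 6. Table 6 itself supports this: its Baseline row covers Day 1 only, yet SES-CD is never scheduled on Day 1, so its baseline has to come from SAP 3.1.1. Protocol 8.1 accepts unscheduled pre-dose values. It also builds composite baselines from component baselines whether or not these were taken at the same visit. The ideal-weight formula sets no window, and SAP 3.1.3 introduces its windows for summarizing clinical data, whereas height is a one-time demographic.

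Much of this stands. A reader might infer from SAP 3.1 and 3.1.3 that early heights are definitely barred; the documents do not establish that. Nor do they settle the opposite. SAP 3.1.1 speaks of efficacy and safety variables in general terms and does not name height, which SAP 3.2.2 lists under demographics. It omits the protocol's express admission of unscheduled values. The SAP nowhere ranks the two rules.

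A reader might also infer that baseline SES-CD would be lost and subjects turned into endoscopic non-responders. The timeline in step 7 makes that at most a one-day edge case, so SES-CD is not realistically affected.

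**Conclusion.** Wrong as written, minor severity. The Screening start in Table 6 contradicts the SAP's own text and the protocol by 7 days. Compliant Stage 1 data from Day -35 to -29 are left out on a literal reading and kept if SAP 3.1.1 governs, and the SAP does not choose. Height is the main variable exposed, and through it the CDAI weight item, BMI and ideal-weight creatinine clearance.

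The primary result is not threatened. Under the assumptions in steps 4 and 5 (illustrative heights and weights, a 2 kg weight change, the other seven items summed), an affected subject's change score moves by about 2.4 to 4.2 points. Level-based criteria at 150 and 300 could shift more. The 20% should not be read as the proportion of subjects affected: the documents give no count of subjects screened that early.

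**What to change.** In Table 6 of SAP 3.1.3, change the Screening start from -28 to -35. All 35 permitted days are then windowed and none becomes unscheduled. Add one sentence stating that baseline values and variables collected only at screening, such as height, follow SAP 3.1.1 regardless of window. The cost is one number and one sentence. Data collection, sample size and power do not change.
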